16.3 Description of study population

16.3.1 *Demographics and baseline characteristics*

Demographics, weight and height will be presented by treatment through descriptive statistics.

16.3.2 *Medical/surgical history and prior/concomitant medication*

Medical/surgical history will be presented by SOC and preferred term (PT). Prior/concomitant medications will be presented by ATC level 1, 3 and 5.

All data will be listed by subject.

16.3.3 *History of nicotine use*

History of nicotine use will be presented through descriptive statistics and listings.

16.3.4 *Treatment compliance*

The number of subjects treated with each treatment period will be listed.

16.3.5 *Physical examination*

Abnormal findings will be specified and presented by subject through descriptive statistics.

16.4 Analysis of primary endpoints

16.4.1 *In vivo extracted fraction of nicotine*

The data needed for the analysis of in vivo extracted amount of nicotine are the individual data of amount of nicotine for unused reference pouches and the amount of nicotine left in the study pouches. The difference between the nicotine content of the reference pouch and the study pouch will be used to calculate the extracted amount. The mean of extracted amount (mg/unit) and fraction (%) of nicotine for each IP pouch, will be calculated. The extracted fraction of nicotine will be analyzed using the linear mixed-effects analysis of variance (ANOVA) model with fixed effects for product, and a random effect for subject. A 90% confidence interval which lies between 0.8 to 1.25 will be judged as equivalent.

Amount and fraction of nicotine in reference pouches and in used pouches will be presented through descriptive statistics.

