The extracted fraction of nicotine for primary objective will be analyzed using the linear mixed-effects analysis of variance (ANOVA) model with fixed effects for product, and a random effect for subject with a confidence interval of 90%.

Study reporting

After completion of the study, an International Council for Harmonisation (ICH) E3 compliant clinical study report (CSR) will be prepared.

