8 STUDY DESIGN

8.1 Overall study design and schedule of events

This is an open, randomized, nine-way cross-over, single dose administration study designed to assess in vivo extraction of nicotine and/or flavor compounds of non-tobacco-based nicotine pouches. The study will include 36 subjects.

The study will include a screening visit, two treatment visits for administration of in total 9 doses of IP, and a follow-up (FU) telephone visit.

Screening (Visit 1) will take place within 28 days prior to Visit 2 and will include an eligibility check including review of health status and evaluation of nicotine/tobacco use, see Table 8-1 for details.

Subjects shall be abstinent from snus and all other nicotine containing products for at least 12 hours before each treatment visit and are instructed to abstain from snus, cigarettes, or other nicotine delivery products as from 8.00 p.m. the evening before each treatment visit. The subjects should certify abstinence at the beginning of each treatment visit. The two treatment visits start with administration of one IP dose for the primary objective and are performed during the morning hours to facilitate abstinence. The subjects are instructed not to eat, drink, chew chewing gum, use nicotine free pouches or brush teeth from 30 minutes before and during

application of the IP [3]. Following administration of 3 or 4 doses of IP, according to a pre-determined randomized order, with at least 60 minutes between doses (from end of administration to start of administration).

The IPs are administered as single doses and the subject keeps the pouch still between the upper lip and the gum for 60 minutes and are instructed not to manipulate the pouch with the tongue or lips. After 60 minutes the pouches are collected and frozen (-20°C) pending analysis of residual nicotine and flavor compound content.

Table 8-1 Schedule of events

Visit Assessment / Study days	Refer to CSP section:	Screening	Treatment visits		Follow up
		Visit 1 Day -28 to Day 1	Visit 2 Day 1	Visit 3 ≥1 day after Day 1	Visit 4 (Phone call) 5 days (-3/+3) after last dose ¹
Informed Consent	13.3	X			
Inclusion/exclusion criteria	9.4, 9.5	X			
Demographics	11.2	X			
Medical/surgical history	11.2.4	X			
History of nicotine use	11.2.5	X			
Weight/height (BMI)	11.2.6	X			
Physical Examination	11.2.7	X			
Alcohol test ²	11.2.8	X	X		
Urine Drug Screen ²	11.2.9	X	X		
Pregnancy Test ³	11.2.10	X	X		
Randomization	9.9		X		
IP treatment ⁴	10.5		X ⁵	X ⁵	

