9.9 Randomization

On Visit 2, the subjects will be randomized to a treatment sequence consisting of the nine IP doses, see Table 9-1. The randomized treatment sequence at Visit 2 and 3 will start with either of treatment A or treatment B (to facilitate abstinence for the primary objective, see Section 8.1). A computer-generated randomization list will be created using SAS Proc Plan, SAS Version 9.4. The randomization list will contain subject number, treatment sequence, period, and treatment. As this is an open study, the treatment sequence to which each subject is allocated will be recorded in the eCRF.

The randomization list will be generated by CTC or delegate and provided to the packing company. The original randomization list will be kept by the randomizer. A copy of the randomization list will be provided to the clinic.

Table 9-1 *IP treatments and type of extraction*

Label	Treatment (type of extraction)
A	ZYN Moist Wintergreen (1) (nicotine extraction)*
B	ZYN Moist Smooth (nicotine extraction)
C	ZYN Moist Wintergreen (1) (flavor extraction)*
D	ZYN Moist Wintergreen (2) (flavor extraction)*
E	ZYN Moist Chill (flavor and nicotine extraction)
F	ZYN Moist Cool Mint (flavor extraction)*
G	ZYN Moist Citrus (flavor and nicotine extraction)
H	ZYN Moist Spearmint (flavor and nicotine extraction)
I	ZYN Moist Deep Freeze (flavor and nicotine extraction)

*Combined analysis of nicotine and flavor compound is not possible

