16.2 Determination of sample size

The main hypothesis is to show that the fraction of extracted nicotine in ZYN Wintergreen is equivalent to that of Zyn Smooth.

Former studies (SM-17-03 and SM 18-01) has shown that the fraction of extracted nicotine has a mean CV of 31%, using a power of 80% and a 90% confidence interval (0.8-1.25) for the ratio will give a sample size of 33 subjects needed to show equivalence between the ZYN Wintergreen and ZYN Smooth (using Proc Power in SAS). In order for a small number of dropout will 36 subjects be included.

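### The primary model has no visit term, although Wintergreen (1) and Smooth are always compared across two different visits

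*Protocol*

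**What the plan says.** Section 16.4.1 specifies a "linear mixed-effects analysis of variance (ANOVA) model with fixed effects for product, and a random effect for subject", with equivalence concluded if the 90% confidence interval lies within 0.8 to 1.25. The synopsis gives the same model: "fixed effects for product, and a random effect for subject with a confidence interval of 90" per cent. Neither place has a visit, period or sequence term.

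On timing, section 8.1 says: "The two treatment visits start with administration of one IP dose for the primary objective". Section 9.9 says: "The randomized treatment sequence at Visit 2 and 3 will start with either of treatment A or treatment B", and its table labels Wintergreen (1) for nicotine extraction as A and Smooth as B. Section 10.5 gives each product once. The schedule of events puts Visit 3 at "≥1 day after Day 1".

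On allocation, section 9.9 says: "A computer-generated randomization list will be created using SAS Proc Plan, SAS Version 9.4". It adds: "The randomization list will contain subject number, treatment sequence, period, and treatment". No AB:BA ratio or blocking is stated. Section 9.8.3 makes replacement of withdrawn subjects optional.

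On sample size, section 16.2 says that the extracted fraction "has a mean CV of 31%, using a power of 80% and a 90% confidence interval (0.8-1.25) for the ratio" leads to 33 evaluable subjects, with 36 included to allow for dropout.

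**The concern.** No single sentence says that A and B fall at different visits, but sections 8.1, 9.9 and 10.5 together leave no other reading: one primary-objective dose opens each visit, it is A or B, and each is given once. A subject's A–B difference therefore carries any systematic difference between Visit 2 and Visit 3, with one sign in the AB order and the opposite sign in the BA order.

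A model with product and subject only cannot separate that difference. With equal numbers in the two orders it cancels from the estimated ratio but stays in the residual, so the interval is wider than necessary. With unequal numbers, part of it also shifts the ratio. In an equivalence trial such a shift can raise the chance of a false equivalence claim.

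**Working it through.** **Inputs.** From section 16.2: CV 31%, power 80%, 90% interval, limits 0.8 to 1.25, 33 evaluable and 36 included. Assumptions: 31% is a within-subject CV, the analysis is on the log scale, and the true ratio is 1.00 (this set reproduces the plan's number). The Visit 3/Visit 2 ratio is not in the protocol; 1.10 and 1.20 are shown. The AB/BA split is not stated; several are shown.

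**Step 1: reproduce the plan's number.**
- Within-subject log variance: ln(1 + 0.31²) = 0.0918.
- Variance of the A–B log difference: 2 × 0.0918 = 0.1835.
- Two one-sided tests at 5% each, n − 1 degrees of freedom (no visit term): power 0.7837 at n = 32 and 0.8006 at n = 33. The stated 33 is reproduced.

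**Step 2: effect on the residual.** Let π = ln(Visit 3/Visit 2). The A–B difference has mean τ − π in order AB and τ + π in order BA. Near balance, a model without visit adds π² to the variance of the difference.
- 10% effect: (ln 1.1)² / 0.1835 = 0.00908 / 0.1835 = 5.0%; the interval is √1.050 = 1.02 times as wide.
- 20% effect: (ln 1.2)² / 0.1835 = 0.03324 / 0.1835 = 18.1%; the interval is √1.181 = 1.09 times as wide.

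**Step 3: effect on the ratio.** Bias on the log scale = π × (n_BA − n_AB) / n. For a 10% effect (π = 0.0953) and more subjects in AB:
- 18/18: none.
- 18/15: exp(−0.0953 × 3/33) = 0.991, a bias of about 0.9%.
- 20/13: exp(−0.0953 × 7/33) = 0.980, a bias of about 2%.

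**Step 4: power and type I error by simulation.** Power is at a true ratio of 1.00. Type I error is at the worse of the two limits, nominal 0.05.

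| AB/BA split | Visit effect | Power, no visit term | Type I error, no visit term | Power, visit term |
|---|---|---|---|---|
| 17/16 | 10% | 0.79 | 0.05 | 0.80 |
| 17/16 | 20% | about 0.75 | 0.04 | 0.80 |
| 18/15 | 10% | 0.78 | 0.06 | 0.80 |
| 20/13 | 10% | 0.77 | 0.08 | about 0.78 |
| 20/13 | 20% | 0.69 | 0.10 | about 0.78 |
| 18/18 | 10% | 0.83 | about 0.046 | 0.84 |
| 18/18 | 20% | 0.79 to 0.80 | below 0.04 | 0.84 |

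With the visit term, type I error is about 0.05 in every row. Under simple randomization, 33 subjects would split 20/13 or worse with probability 0.30.

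**Step 5: cost of the term.** With n − 2 degrees of freedom, power at n = 33 is 0.7999 instead of 0.8006. The formal requirement becomes 34, and power at the planned 36 is 0.844.

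**The case against.** The strongest reply is that the design already removes most time-related differences between A and B. Both occupy the same slot, the first dose of the morning after at least 12 hours without nicotine, and pouches are collected at 60 ± 1 minutes. Subjects are experienced daily users. No visit effect is documented, and with balanced order the omission is conservative: the sponsor loses power and the equivalence claim stays valid. Section 16 also describes itself as principal features, with detail left to a SAP that is not shown.

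Much of this stands. A visit effect may be small, and with balanced order and a 10% effect the loss is about one point of power. From an 18/18 start, losing the three subjects allowed for gives 18/15 at worst, so a 20/13 split cannot come from planned dropout. It would need unbalanced allocation.

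The appeal to the SAP is weaker. The protocol names the model's terms twice, so a SAP that adds visit would depart from the stated model.

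Three stronger readings lack support:
- A reader might infer that assay batch differs by visit. Pouches are frozen pending analysis, and nothing ties batches to visits.
- A reader might infer that products E, G, H and I, given in later slots, enter the residual of the primary model. The synopsis ties the model to the primary objective, which is A versus B. Section 16.4.1 does not repeat the restriction, so it is worth stating, but the inference is not established.
- A reader might take a smaller variance (for example 0.0897 for the difference, treating 31% as a total CV with correlation 0.5), where the relative inflation doubles to 10% and 37%. That variance does not reproduce 33 subjects, and at it power stays about 0.97 even with a 20% visit effect.

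**Conclusion.** The point holds as a moderate improvement to the primary analysis. The protocol fixes a model without visit for what is in effect a two-period AB/BA crossover, although period is already on the randomization list.

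The size rests on an assumed visit effect. At the variance that reproduces the plan's 33 subjects and near-equal orders, the cost is about one point of power for a 10% effect and about five points for a 20% effect. For a 10% effect, bias and type I error become a modest concern at 18/15 (0.9%, about 0.06) and a clearer one at 20/13 (2%, about 0.08).

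A reader might conclude that the primary result will be biased. The protocol does not support that: bias needs both a visit effect and unequal orders, and it establishes neither.

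**What to change.** - In the synopsis and section 16.4.1, add visit (2 or 3) as a fixed effect in the primary model, keeping product as fixed and subject as random.
- State in section 16.4.1 that this model is fitted to doses A and B only.
- State in section 9.9 that the list balances the order of A and B, 18 subjects AB and 18 BA.

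A sequence term is optional; it does not change the within-subject A–B contrast when both doses are observed.

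The cost is wording, settled before database lock, and one residual degree of freedom (32 to 31 at n = 33). The planned 36 subjects cover it, and no new data are needed.

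### The primary model estimates a difference, but the equivalence limits of 0.8 to 1.25 are for a ratio, and the protocol does not say how the ratio is obtained

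*Protocol*

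**What the plan says.** Section 16.4.1 of the protocol fixes three things for the primary comparison of Wintergreen (1) with Smooth.

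- Response and model: "The extracted fraction of nicotine will be analyzed using the linear mixed-effects analysis of variance (ANOVA) model with fixed effects for product", with subject as a random effect. The fraction is expressed in %.
- Pass rule: "A 90% confidence interval which lies between 0.8 to 1.25 will be judged as equivalent". The sentence does not say what quantity the interval is for.
- Descriptive summaries. Section 16.1 lists the arithmetic mean and SD among them, but no geometric mean or geometric CV.

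The synopsis repeats the model, "a random effect for subject with a confidence interval of 90" percent, without naming a scale or any limits.

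Section 16.2 is the only place that names the scale. It starts from earlier studies in which "the fraction of extracted nicotine has a mean CV of 31" percent, and continues: "using a power of 80% and a 90% confidence interval (0.8-1.25) for the ratio will give a sample size of 33 subjects". It then adds three subjects for dropout, making 36.

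The introduction to section 16 says that only principal features are given there, and that an SAP will elaborate on them and be signed before the database is locked. The SAP is not among the documents at hand.

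**The concern.** A linear mixed model with product as a fixed effect returns a difference between product means in the units of the response. If the response is the fraction in %, that is a difference in percentage points, and equality is 0. The limits 0.8 and 1.25 are a pair around 1 and make sense only for a ratio. To join the two, the analyst must either log the response and back-transform the contrast, or form a ratio of means from the untransformed model by a method such as Fieller. The protocol states neither.

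This is the only confirmatory decision in the trial, so the estimand behind it should be fixed. The two routes target different quantities (geometric against arithmetic mean ratio) and do not have the same power. The study is open-label, the sponsor takes part in analysing the pouches (section 11.3.1), and the SAP need only be signed before database lock. The protocol therefore allows the choice to be made after residual-nicotine results exist.

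**Working it through.** **Inputs.** From section 16.2: CV 31%, power 80%, 90% interval (two one-sided 5% tests), ratio limits 0.8 and 1.25, n = 33, 36 included. Assumed, because the protocol does not give them: true ratio 1.00; 31% is a within-subject CV, so the two pouches of one subject have correlation 0 on top of it; only the two primary products enter the comparison, so df = n − 1.

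**Step 1: reproduce the stated sample size on the log scale.**

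- SD of the log fraction: √ln(1 + 0.31²) = 0.3029.
- SD of the within-subject log difference: 0.3029 × √2 = 0.4284.
- Standard error at n = 33: 0.4284 / √33 = 0.0746.
- Limits: ±ln 1.25 = ±0.2231.
- Expected 90% half-width: 1.694 × 0.0746 = 0.126, i.e. a ratio interval of about 0.88 to 1.13 around 1.00.
- Exact power of the two one-sided tests: 78.4% at n = 32, 80.1% at n = 33, 84.4% at n = 36.

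So 33 is the smallest n that reaches 80%. With n − 2 degrees of freedom, as in a two-period crossover, power at 33 is 79.99% and the answer is 34. The stated figure is thus what a log-ratio analysis gives.

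**Step 2: the other way to a ratio.** Keep the fraction untransformed and test the ratio of arithmetic means by Fieller. Equivalence is concluded if the mean of (A − 0.8 B) is significantly above 0 and the mean of (A − 1.25 B) significantly below 0, each at one-sided 5%. Simulated with CV 31%, true ratio 1.00 and correlation 0:

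| Analysis | n = 33 | n = 36 |
|---|---|---|
| Log scale, ratio of geometric means | 80.1% | 84.4% |
| Untransformed, ratio of arithmetic means (normal data) | about 76% | about 81% |
| Untransformed, ratio of arithmetic means (lognormal data) | about 78% | about 82% |

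The choice is worth about 2 to 4 points of power. With a correlation of 0.5 on top of the 31%, both exceed 97% at n = 33 (98.7% log; 97.9% Fieller, normal data), and the gap is under one point.

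**Step 3: the rule applied literally to the model contrast.** The 90% half-width in percentage points is 1.694 × f × 0.31 × √(2(1 − ρ)) / √33, where f is the mean extracted fraction in %. The protocol gives no value for f; assume 30 to 50.

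- f = 30: 3.9 points at ρ = 0, 2.7 points at ρ = 0.5.
- f = 50: 6.5 points at ρ = 0, 4.6 points at ρ = 0.5.

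The window from 0.8 to 1.25 is 0.45 wide and excludes 0. No interval with these half-widths fits inside it. This shows that the contrast and the limits cannot be on the same scale; it does not predict the trial's outcome.

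**The case against.** The strongest reply is that the protocol does supply the scale. Section 16.2 attaches the same limits and the same interval level to a ratio for the same comparison, and a linear mixed ANOVA is routinely run on logged data. Section 16.4.1 never says that the fraction is untransformed; that reading rests on silence. Transformation and interval method are also things that an SAP commonly settles, and one is promised before database lock.

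Much of this stands. The intent to use a ratio is plain, and the sample size supports it. A reader might infer from the literal text that two identical products could never pass, so that power is 0% instead of 80%. The documents do not support that: it requires ignoring section 16.2 and comparing a percentage-point difference with ratio limits. Nor do they support a claim that the sample size is wrong.

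What does not stand is that the matter is therefore settled or merely SAP detail. Knowing that a ratio is meant does not say which ratio. The protocol has itself fixed a response and a pass rule, and these do not fit each other. An SAP that introduced a log transformation would be changing the stated response. Signing before lock is also not the same as signing before laboratory results exist.

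**Conclusion.** The point holds as a mismatch of scale between the stated primary model and the stated decision rule. The practical consequence is an unfixed ratio estimator for the one confirmatory claim. It is modest in size: at n = 33, 80.1% power for the log-scale ratio against about 77% for a ratio of arithmetic means, and 84.4% against 81 to 82% at the planned 36. These figures assume a true ratio of 1.00, correlation 0 and a within-subject CV of 31%, none of which the protocol confirms; a positive correlation on top of the 31% narrows the gap. Sample size, limits, interval level and design are not in question. Because the decision is the primary one and the correction is nearly free, it should be made before results are available.

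**What to change.** In section 16.4.1, and in the matching sentence of the synopsis, state that:

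1. the natural logarithm of the extracted fraction is the response in the mixed model;
2. the difference in least-squares means, treatment A (Wintergreen (1)) minus treatment B (Smooth), and its 90% confidence interval are back-transformed to a ratio of geometric means;
3. equivalence is concluded if the whole 90% interval for that ratio lies within 0.80 to 1.25.

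Do not add a rule that switches to a ratio of arithmetic means when some observed fraction is zero or negative. That would let the data choose the estimand, and nothing in the protocol suggests that such values are expected.

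The cost is a few sentences in the protocol, carried into the SAP. The sample size stays at 33 evaluable and 36 included, and nothing changes in the conduct of the study.

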16.5 Analysis of secondary endpoints

16.5.1 *In vivo extracted amount and fraction of nicotine*

The data needed for the analysis of in vivo extracted amount of nicotine are the individual data of amount of nicotine for unused reference pouches and the amount of nicotine left in the study pouches. The difference between the nicotine content of the reference pouch and the study pouch will be used to calculate the extracted amount. The mean of extracted amount (mg/unit) and fraction (%) of nicotine for each IP pouch, will be calculated. The extracted dose of nicotine will be analyzed using the signed Wilcoxon rank sum test for within subject difference (i.e. between IPs).

Amount and fraction of nicotine in reference pouches and in used pouches will be presented through descriptive statistics.

16.5.2 In vivo extracted amount and fraction of flavor compound

The data needed for the analysis of in vivo extracted amount and fraction of flavor compound are the individual data of amount of flavor compound for unused reference pouches and the amount of flavor compound left in the study pouches. The difference between the flavor compound content of the reference pouch and the study pouch will be used to calculate the extracted amount (mg/unit) and fraction (%). The mean of extracted amount (mg/unit) of flavor compound for each IP pouch, will be calculated.

Amount and fraction of flavor compound in reference pouches and in used pouches will be presented through descriptive statistics.

16.5.3 Analysis of Adverse events

An overview of all AEs, including SAEs, intensity, and deaths will be presented by SOC and PT.

All AE data will be listed subject include the verbatim term entered by the Investigator.

